8.5.3.3 Serum Titers of Anti-MSB0011359C Antibodies (ADA)

Immunogenicity testing strategy will be implemented and conducted in line with:

- Immunogenicity Assessment of Biotechnology-Derived Therapeutic Proteins (EMA/CHMP/BMWP/14327/2006).
- Immunogenicity assessment of monoclonal antibodies intended for in vivo clinical use (European Medicines Agency [EMA]/CHMP/BMWP/86289/2010).
- Food and Drug Administration (2009, draft) Guidance for Industry: Assay Development for Immunogenicity Testing of Therapeutic Proteins.

A qualified method that uses an acid dissociation step to detect ADAs in the presence of excess drug in human serum will be applied. Removal of drug after acid treatment is not required. The ADA titers of positive samples will be determined.

CCI

8.5.4 Analysis of Safety

The extent of exposure to MSB0011359C will be characterized by duration (weeks), number of administrations, cumulative dose (mg/kg), dose intensity (mg/kg/week), relative dose intensity (actual dose given/planned dose), and number of dose delays.

Safety analyses will be performed on the Safety Analysis Set. The safety endpoints will be tabulated by dose-level or cohort, using descriptive statistics.

Safety assessments will be based on review of the incidence of AEs, including AEs of special interest, treatment-related AEs, and changes in vital signs, ECGs, body weight, and laboratory values (hematology and serum chemistry).

8.5.4.1 Adverse Events

Adverse events will be coded according to MedDRA. Severity of AEs will be graded using the NCI-CTCAE v4.03 toxicity grading scale.

The incidence of treatment-emergent AEs regardless of attribution and AEs defined as related to MSB0011359C will be summarized by Preferred Term and System Organ Class, and described in terms of intensity and relationship to MSB0011359C. Adverse events (serious and nonserious) will be considered treatment-emergent adverse events when emerging in the on-treatment period defined as the time from the first trial drug administration to the last drug administration date + 30 days or the earliest date of subsequent anticancer drug therapy minus 1 day, whichever occurs first, unless otherwise stated. All premature terminations will be summarized by primary reason for treatment withdrawal.

8.5.4.2 Laboratory Variables

Laboratory results will be classified by grade according to NCI-CTCAE v4.03. The worst on-trial grades after the first trial treatment will be summarized. Shifts in toxicity grading from first treatment to highest grade will be displayed. Results for variables that are not part of NCI-CTCAE will be presented as within or above normal limits. Only subjects with post-Baseline laboratory values will be included in these analyses.

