3.5.2 Immune-related Adverse Events / Autoimmune Disorders

Immune-related AEs are AESIs.

The following irAEs are important identified risks for MSB0011359C.

- Immune-related pneumonitis
- Immune-related hepatitis
- Immune-related colitis
- Immune-related nephritis and renal dysfunction
- Immune-related endocrinopathies (thyroid disorders, adrenal insufficiency, type 1 diabetes mellitus, pituitary disorders)
- Immune-related rash
- Other immune-related events (myositis, myocarditis, encephalitis)

The following irAEs are important potential risks for MSB0011359C:

- Guillain-Barré syndrome
- Uveitis
- Pancreatitis
- Myasthenia gravis/myasthenic syndrome

Immune-related AEs / autoimmune disorders are events that are related to the pharmacology of checkpoint inhibitors and can be explained by an immune-phenomenon after other etiologies have been ruled out. Relevant clinical safety experience has been generated with the parent anti-PD-L1 avelumab antibody.

- As of 05 November 2014, a cumulative review revealed 56 cases of potential irAEs out of 480 subjects (11.7%) treated in the dose-expansion part of Trial EMR 100070-001 and 4 cases out of 50 subjects (8.0%) treated in the dose-escalation part of Trial EMR 100070-001. A

customized Medical Dictionary for Regulatory Activities (MedDRA) query was used for data retrieval from the clinical database with predefined Preferred Terms of potential irAEs.

- Of 69 potential irAEs reported, 13 were SAEs (18.8%) and 56 were nonserious AEs (81.1%). In the majority of the cases, there was a plausible temporal association between the event onset and the drug administration. Of these 69 events, 46 events (66.7%) were assessed as treatment-related by the Investigator and 23 events (33.3%) were assessed as not treatment-related by the Investigator.
- Twenty-six events were assessed as Grade 1, 29 events as Grade 2, 11 events as Grade 3, 2 events as Grade 4, and 1 event (pneumonitis) as Grade 5 (note: 2 more events of autoimmune hepatitis had a fatal outcome; however, they were assessed as Grade 3 with a subsequent fatal liver failure).
- Based on the irAE cases that have been observed with avelumab, all trial Investigators will be trained to be made aware of the frequency and severity of the observed events and to proactively administer steroid treatment for any suspicion of irAEs.

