- A basic urinalysis will be performed prior to trial treatment every according to [Table 2](#)
- Samples for ANAs and RF according to [Table 2](#)
- A serum HCG pregnancy test will be required at Screening, urine or serum β -HCG pregnancy test will be performed according to [Table 2](#). Results of the most recent pregnancy test should be available prior to next dosing (if applicable)

- The tumor evaluation (see Section 7.3) will be performed at Week 7, and then once every 6 weeks, with a tumor assessment visiting time window of 5 days prior to dosing. For subjects continuing treatment beyond 12 months (in consultation with the Medical Monitor), tumor evaluations should take place every 12 weeks
- Mandatory on-treatment biopsy should be performed at Week 3 within 7 days after the Week 3 IMP administration for the NSCLC biomarker cohort. A mandatory Week 7 biopsy should be performed within 7 days after the Week 7 IMP administration for the NSCLC anti-PD-1 / PD-L1 failure (if possible) and the melanoma anti-PD-1 / PD-L1 failure cohort (if possible), as detailed in Table 3
- PK samples will be drawn as detailed in Table 3
- Free T4 and TSH will be measured prior to trial treatment according to Table 2
- ADA samples will be drawn as detailed in Table 3. The term for ADA on the CRF is human-antihuman antibodies (HAHA)
- The immunomonitoring and soluble factors will be performed as detailed in Table 3 as described in Section 7.6.1.2
- Samples for TGF β determination will be drawn as detailed in Table 3
- Samples will be collected for viral load testing (HBV, HCV) and alpha-fetoprotein from subjects in the HCC second-line cohort (both ascending dose and expansion) as detailed in Table 3
- CCI [REDACTED]

Note: After at least 50 subjects across the dose escalation and all expansion cohorts have been evaluated for safety by the SMC, with appropriate SMC safety recommendation and if the Sponsor considers PK characterization adequate, then Day 2, 8, and 22 visits may be skipped.

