## 15.3 Clinical Laboratory Evaluation

### 15.3.1 Hematology and Chemistry Parameters

Baseline Laboratory Assessments are defined as the last non-missing observation prior to first dose of trial treatment, while Treatment Emergent Laboratory Assessments are any sample collected after 1st drug administration and within the on-treatment period as defined in Section 9.8. Laboratory values (including corresponding normal ranges) converted in standard unit will be used for listings. Laboratory results will be classified according to the NCI-CTCAE criteria version 4.03. Non-numerical qualifiers (with exception of fasting flags) will not be taken into consideration in the derivation of CTCAE criteria (e.g., hypokalemia Grade 1 and Grade 2 are only distinguished by a non-numerical qualifier and therefore Grade 2 will not be derived, similar for Grade 1 and Grade 3 hyperuricemia where Grade 3 will not be derived). Additional laboratory results that are not part of NCI-CTCAE will be categorized as follows: below normal limits, within normal limits, and above normal limits.

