**Table 8 NCI-CTC Gradable parameters**

Parameter (LBTEST)	Parameter code (LBTESTCD)	Name in NCI-CTC	Direction of abnormality
Biochemistry			
Alanine Aminotransferase	ALT	Alanine aminotransferase increased	High
Albumin	ALB	Hypoalbuminemia	Low
Alkaline Phosphatase	ALP	Alkaline phosphatase increased	High
Amylase	AMYLASE	Serum amylase increased	High
Aspartate Aminotransferase	AST	Aspartate aminotransferase increased	High
Bilirubin	BILI	Blood bilirubin increased	High
Calcium	CA	Hypercalcemia/Hypocalcemia	High/Low
Cholesterol	CHOL	Cholesterol high	High
Creatinine	CREAT	Creatinine increased	High
Gamma Glutamyl Transferase	GGT	GGT increased	High
Glucose	GLUC	Hyperglycemia/Hypoglycemia	High/Low
Haptoglobin 	HAPTOG	Haptoglobin decreased	Low
Lipase	LIPASET	Lipase increased	High
Magnesium	MG	Hypermagnesemia/Hypomagnesemia	High/Low
Phosphate	PHOS	Hypophosphatemia	Low

Parameter (LBTEST)	Parameter code (LBTESTCD)	Name in NCI-CTC	Direction of abnormality
Potassium	K	Hyperkalemia/Hypokalemia	High/Low
Sodium	SODIUM	Hypernatremia/Hyponatremia	High/Low
Triglycerides	TRIG	Hypertriglyceridemia	High
Urate	URATE	Hyperuricemia	High
Hematology			
Activated Partial Thromboplastin Time	APTT	Activated partial thromboplastin time prolonged	High
Hemoglobin	HGB	Anemia/Hemoglobin increased	Low/High
Leukocytes	WBC	Leukocytosis/White blood cell decreased	High/Low
Lymphocytes	LYM	Lymphocyte count decreased/Lymphocyte count increased	High/Low
Neutrophils	NEUT	Neutrophil count decreased	Low
Platelets	PLAT	Platelet count decreased	Low
Prothrombin Intl. Normalized Ratio	INR	INR increased	High

 Haptoglobin is collected only in case of episode of anemia. It will be described in listings only.

For **WBC differential counts** (neutrophil, lymphocyte counts), the absolute value will be used when reported. When only percentages are available (this is mainly important for neutrophils and lymphocytes, because the CTCAE grading is based on the absolute counts), the absolute value is derived as follows:

$$\text{Derived differential absolute count} = (\text{WBC count}) * (\text{Differential \%value} / 100)$$

If the range for the differential absolute count is not available (only range for value in % is available) then Grade 1 will be attributed as follows:

- Lymphocyte count decreased:
  - derived absolute count does not meet Grade 2-4 criteria, and
  - % value < % Lower Limit of Normal (LLN) value, and
  - derived absolute count  $\geq 800/\text{mm}^3$

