**Table 9 Non-NCI-CTC Gradable Parameters**

Parameter (LBTEST)	Parameter code (LBTESTCD)
Biochemistry	
Blood Urea Nitrogen	BUN
C Reactive Protein	CRP
Chloride	CL
Creatine Kinase	CK
Creatinine Clearance 	CREATCLR
Indirect Bilirubin 	BILIND
Lactate Dehydrogenase	LDH
Protein	PROT
Urea 	UREA
Hematology	
Basophils/Leukocytes	BASOLE
Eosinophils/Leukocytes	EOSLE
Ery. Mean Corpuscular HGB Concentration	MCHC
Ery. Mean Corpuscular Hemoglobin	MCH
Ery. Mean Corpuscular Volume	MCV
Erythrocytes	RBC
Hematocrit	HCT
Monocytes/Leukocytes	MONOLE
Prothrombin Time	PT
Reticulocytes/Erythrocytes	RETIRBC

 Creatinine clearance is only collected at screening to check inclusion criteria. It will be presented in listings only.

 Indirect bilirubin is not measured but obtained by site calculation (=Total bilirubin – Direct bilirubin). It will be presented in listings only.

 Total urea is collected in Europe only (in the US, Blood Urea Nitrogen is collected instead).

Separate listings of Hematology and Biochemistry with onset date after the CSR cutoff (i.e. between 15MAY 2020 and 14MAY 2021) will be created. Each listing will include assigned cohort, participant identifier, age, gender, race, first dose date, last dose date, dose, number of doses, laboratory parameter (units), visit, date, SI value, LLN, ULN, Indicator of Normal Range (Low, Normal, High), and toxicity grade. These listings will be sorted by cohort, participant identifier, and laboratory measurement date.

---

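### Protocol 8.5.4.2 has no below-normal category for laboratory variables outside CTCAE, so low TSH and free T4 would be listed but not summarised

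*Protocol*

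**What the plan says.** Protocol 8.5.4.2 treats laboratory data in two ways. Variables with a CTCAE grade are summarised by worst grade and by shift in grade. For the rest, "Results for variables that are not part of NCI-CTCAE will be presented as within or above normal limits". No shift is described for this second group.

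TSH and free T4 are scheduled at Screening, during treatment and at the safety follow-up visits (protocol Tables 1 and 2). For the expansion cohorts, Section 7.1.2.2 states: "Free T4 and TSH will be measured prior to trial treatment according to" Table 2. Section 3.5.2 names thyroid and pituitary disorders among the important identified risks and gives regular laboratory testing as one of the risk measures. In the endocrine part of protocol Table 7, the entry for asymptomatic TSH abnormality names a low threshold (0.5 × LLN) beside a high one (2 × ULN).

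SAP 15.3.1 has a different rule for ungraded results: "below normal limits, within normal limits, and above normal limits". The parameters that it covers are listed in SAP Table 8 (gradable) and Table 9 (non-gradable). The laboratory output that it then specifies is "Separate listings of Hematology and Biochemistry with onset date after the CSR cutoff".

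**The concern.** A rule with only two categories suits a variable for which harm lies in the high direction. TSH and free T4 can be abnormal in either direction, and the protocol recognises this for TSH in Table 7. So the plan collects a test for an identified risk, names a low threshold for it, and then has nowhere in the laboratory summary to count a value below that threshold. The reader of a safety table would see no incidence of low values and no shift from baseline towards low.

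The two documents also give different rules for the same class of variable. SAP Section 7, which records changes from the protocol, mentions only that there will be no final analysis. The difference is therefore neither explained nor resolved.

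**Working it through.** There is no alpha, power or sample size to reproduce. The check is of the text, plus a count of patterns.

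**1. Does the two-category rule reach TSH and free T4?** SAP Table 8 has 19 biochemistry and 7 hematology rows (26). Table 9 has 9 and 10 (19). None of the 26 + 19 = 45 rows is TSH or free T4. That they are ungraded is inferred from their absence in Table 8; no document says so. If they are ungraded, 8.5.4.2 applies. There is a narrower reading: protocol 8.5.4 describes the laboratory review as hematology and serum chemistry, and protocol Table 11 places TSH and T4 outside those panels. On that reading they have no planned laboratory summary at all. Neither reading gives a low category.

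**2. What happens to a low value?** With two categories, a programmer can count it as within normal or leave it out. Either way it cannot be seen in the table.

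**3. Which patterns are affected?** Take each test as low, normal or high. A cell is marked yes if at least one test would be counted as above normal.

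| | free T4 low | free T4 normal | free T4 high |
|---|---|---|---|
| TSH low | no | no | yes |
| TSH normal | no | (both normal) | yes |
| TSH high | yes | yes | yes |

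Abnormal cells: 9 − 1 = 8. Cells with something above normal: 3 (TSH high) + 2 (free T4 high, TSH not high) = 5. Cells with nothing above normal: 8 − 5 = 3. These are isolated low TSH, low free T4 with normal TSH, and both low. The last two are the pituitary-type patterns. This counts patterns, not patients.

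**4. Would another summary catch those three?** Protocol 7.4.1.1 keeps an abnormal laboratory finding out of the adverse event data unless it comes with signs or symptoms, leads to treatment discontinuation, or is considered medically important by the investigator. The irAE algorithm in SAP 15.2.3.2 requires, among other criteria, that corticosteroids, immunosuppressants or hormonal therapy were given. A low value that is asymptomatic, untreated, did not end treatment and was not judged important meets neither route.

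**5. Is the value anywhere?** Yes. Protocol 8.5.1 requires individual listings of all recorded data on the Safety Analysis Set.

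**6. Protocol and SAP side by side.**

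| | Protocol 8.5.4.2 | SAP 15.3.1 |
|---|---|---|
| Categories for ungraded variables | within, above | below, within, above |
| Scope | all non-CTCAE laboratory variables | section headed hematology and chemistry |
| TSH and free T4 named | no | no (Tables 8 and 9) |
| Status | current protocol text | CSR addendum only (Section 6), cancelled (Section 6.1) |

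**The case against.** The best defence is that this is a wording slip with little consequence. Several parts of it stand, and each closes off a stronger reading.

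- A reader might infer that low values go unreported. They do not: Section 8.5.1 puts every value in a listing, and clinically relevant cases can enter the adverse event tables. What is missing is a summary category.
- A reader might infer from the SAP tables that the CSR omitted these tests. The documents cannot show that. SAP Sections 5 and 6 say that a separate plan, dated 15 September 2020, governed the CSR. It is not among the documents, and protocol 8.5 defers full details to the analysis plan.
- A reader might size the problem by the class rates in protocol 3.1, about 8% hypothyroidism and 1 to 3% hyperthyroidism. Those are adverse reaction rates for two other drugs. In addition, on usual physiology, primary hypothyroidism shows as high TSH and overt hyperthyroidism as high free T4, and the rule does count both.
- A reader might extend the point to anemia. Hemoglobin is graded in the low direction (SAP Table 8) and anemia is an AESI, so that risk has its own summaries.

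It can also be said that the SAP text already repairs the rule. For TSH and free T4 that is not clear. The three categories sit in a section on hematology and chemistry whose parameter tables omit both tests, and whose stated output is listings for an addendum that was cancelled.

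**Conclusion.** The point holds in a limited form. As written, protocol 8.5.4.2 gives no summary place to low values of ungraded laboratory variables, and no document supplied clearly corrects this for TSH and free T4. The effect falls on three of eight abnormal patterns, and within those on values that also miss the adverse event and irAE routes. How many subjects that would be cannot be derived from the documents.

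The rule has a second, smaller weakness. Even where one test is above normal, the table cannot separate high TSH with low free T4 from high TSH with normal free T4.

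The conclusion rests on two assumptions: that TSH and free T4 are handled as ungraded variables, and that the CSR plan followed the protocol wording. If the CSR plan already used three categories and named both tests, only the protocol text needs aligning. The change is worth making because the rule as stated discards direction for tests tied to an identified risk, and correcting it needs no new data. It concerns tabulation only and touches no clinical threshold or management rule.

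**What to change.** In protocol 8.5.4.2, present ungraded variables as below, within or above normal limits, and add shifts from baseline to the lowest and to the highest post-baseline value. Name TSH and free T4 among the summarised parameters in whichever analysis plan governs the CSR. Amending the tables of the cancelled addendum would achieve nothing. A joint table of TSH by free T4 would show the patterns directly, but is optional.

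The CSR was approved on 2 March 2021. The practical step is therefore to check whether its plan tabulated low TSH and free T4 and, if not, to issue one supplementary table.

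Cost: one phrase and one shift display in the protocol text, two parameter rows in the plan, and at most one extra table, all from data already collected.

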8.5.4.3 Physical Examination, Including Vital Signs and 12-lead Electrocardiogram

Vital signs (body temperature, respiratory rate, heart rate, and blood pressure), eye signs and symptoms based on System Organ Class of “eye disorders”, and 12-lead ECG recorded according to the Schedules of Assessments (refer to [Table 1](#) and [Table 2](#)) will be presented.

Further details will be provided in the SAP based on current safety experience applying the latest MedDRA version.

8.6 Interim and Additional Planned Analyses

Enrollment of expansion cohorts will not be stopped for the purpose of conducting their respective interim analyses but will stop if futility is met as specified.

Dose Escalation Part

In the dose-escalation part, the trial data will be evaluated before decision is made to go to the next dose level or to start with treatment in the expansion part.

Expansion Part

For all expansion cohorts except glioblastoma cohort, the endpoints in these interim analyses are ORR (confirmation is not required). For glioblastoma, the endpoint in the interim analysis will be DCR. There is no multiplicity adjustment is applied to the interim analyses. The decision rules at the interim analyses serve as guidance and are non-binding. In the absence of a control arm, outcomes in this single arm study have to be interpreted with caution, both at interim and final analyses.

CCI

HCC ascending-dose cohort

An interim analysis will be conducted 12 weeks after the final subject in the ascending-dose portion received their first dose.

If ≤ 6 responses are observed in the 30 subjects at the interim analysis, the enrollment into HCC second-line or sorafenib-intolerant cohort will be stopped. This decision criterion has 39% probability of rejecting the null hypothesis if the true response rate is 20% and 6% probability of rejecting the alternative hypothesis if the true response rate is 35%.

Enrollment of HCC second-line or sorafenib-intolerant cohort will not be stopped for the purpose of conducting this interim analysis but will stop if futility is met as specified.

HCC second-line or sorafenib-intolerant cohort

No interim analysis is planned.

NSCLC anti-PD-1 / anti-PD-L1 failure cohort

One interim analysis is planned for this cohort 12 weeks after the 40th subject in this cohort started treatment.

- If ≤ 2 responses are observed in the 40 subjects at the interim analysis, the enrollment will be stopped. This decision criterion has 32% probability of rejecting null hypothesis if the true response rate is 5% and 5% probability of rejecting alternative hypothesis if the true response rate is 15%.
- If 3 to 4 responses are observed at the interim analysis, the enrollment will be temporarily stopped until the first 40 subjects have completed tumor assessment at Week 24. After a review of the totality of data, including duration of response, DCR, and safety, the Sponsor will make a decision as to whether to resume the accrual.
- If ≥ 5 responses are observed at the interim analysis, an additional 40 subjects will be enrolled. With 5 responses and using Bayesian principal, the posterior probability of true ORR being above 15% (alternative hypothesis) is approximately 41% and the posterior probability of true ORR being below 5% (null hypothesis) is approximately 2%.

Melanoma anti-PD-1 / anti-PD-L1 failure cohort

One interim analysis is planned for this cohort 12 weeks after the 30th subject in the cohort started treatment.

NSCLC second-line cohort

There is one planned interim analysis. The primary objective of the interim analysis is to assess the tolerability, safety, and preliminary antitumor activity.

The planned interim analysis will occur 12 weeks after the 30th subject in the cohort started treatment. If ≤ 4 responders are observed at the interim analysis, no further subjects will be enrolled into the NSCLC second-line cohort.

Pancreatic adenocarcinoma second-line cohort

One interim analysis is planned for this cohort 12 weeks after the 30th subject in the cohort started treatment.

CRC third-line cohort

One interim analysis is planned for this cohort 12 weeks after the 30th subject in the cohort started treatment.

SCCHN second-line cohort

One interim analysis is planned for this cohort 12 weeks after the 30th subject in the cohort started treatment.

TNBC second-line cohort

One interim analysis is planned for this cohort 12 weeks after the 30th subject in the cohort started treatment.

Ovarian post-platinum second-line cohort

One interim analysis is planned for this cohort 12 weeks after the 30th subject in the cohort started treatment.

Esophageal post-platinum second-line cohort

One interim analysis is planned for this cohort 12 weeks after the 30th subject in the cohort started treatment.

Glioblastoma second-line cohort

One interim analysis is planned for this cohort 12 weeks after the 30th subject in the cohort started treatment.

Cervical cohort

One interim analysis is planned for this cohort 12 weeks after the 30th subject in the cohort started treatment.

Additional Interim Analyses

In general, interim analyses at time points that are not specified in the protocol may be performed for internal planning purposes.

9 Ethical and Regulatory Aspects

